8.8.3 Activity Classification

The activities in Table 7 will be conducted as prescribed, in a variable order, and will be annotated by the clinician marking the start and stop times for each activity using the Link App. The particular activity performed for a given annotation will be noted on the CRF. This set of activities will be performed 5 times in a random order each time, as listed in the Repetitions column of Table 7.

Table 7: Activity Classification Activities

| Item | Activity | Description | Time | Repetitions | Metric |
|------|-------------------------|--|-------|-------------|--|
| 1 | Standing Classification | Instruct the subject to stand upright. Once the subject is standing upright, start the activity. | 1 min | 5 | ADL Classifier – Standing HR/HRV – Resting |
| 2 | Sitting Classification | Instruct the subject to sit in a chair. Once the subject is sitting, start the activity. | 1 min | 5 | ADL Classifier – Sitting HR/HRV – Resting |
| 3 | Lying Classification | Instruct the subject to lie supine. Once the subject is lying in a supine position, start the activity. | 1 min | 5 | ADL Lying HR/HRV – Resting |
| 4 | Standing Upright | Instruct the subject to stand against the marked wall, with their right side facing the wall. Instruct the subject to stand upright. Once the subject is in position, start the activity. | 1 min | 5 | Posture HR/HRV – Resting |
| 5 | Standing Leaning FRONT | Instruct the subject to stand against the marked wall, with their right side facing the wall. Instruct the subject to lean forward to the 30-degree mark. Once the subject is in position, start the activity. | 1 min | 5 | Posture HR/HRV – Resting |
| 6 | Standing Leaning BACK | Instruct the subject to stand against the marked wall, with their right side facing the wall. Instruct the subject to lean back to the 30-degree mark. Once the subject is in position, start the activity. | 1 min | 5 | Posture HR/HRV – Resting |
| 7 | Standing Leaning RIGHT | Instruct the subject to stand facing the marked wall. Instruct the subject to lean right to the 30-degree mark. Once the subject is in position, start the activity. | 1 min | 5 | Posture HR/HRV – Resting |
| 8 | Standing Leaning LEFT | Instruct the subject to stand facing the marked wall. Instruct the subject to lean left to the 30-degree mark. Once the subject is in position, start the activity. | 1 min | 5 | Posture HR/HRV – Resting |

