8.8.1 Heart Rate Activities

The activities in Table 8 will be conducted as prescribed and will be annotated by the subject marking the start and stop times for each activity using the Link App. The clinician will train the subject on Link App operation and monitor subject performance to ensure that the activities are properly annotated.

Table 8: Heart Rate Activities

| Item | Activity | Description | Time (minimum) | Repetitions | Metric |
|------|----------|--|----------------|---------------------|------------------|
| 1 | Sitting | Sit comfortably in a chair | 22 min | At least 2, up to 4 | HR/HRV – Resting |
| 2 | Walking | Walk on a treadmill at a comfortable pace | 22 min | At least 2, up to 4 | HR/HRV – Moving |
| 3 | Biking | Bike on a recumbent bike at a comfortable pace | 22 min | At least 2, up to 4 | HR/HRV – Moving |

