11.3 Effectiveness Variables

The effectiveness endpoints for this study are the various types of measurements made by the BioStamp nPoint system. All effectiveness endpoints to be statistically summarized will be collected using the BioStamp nPoint during the supervised-use phase. The effectiveness endpoints are as follows:

- Heart Rate (bpm)
- Heart Rate Variability (RMSSD⁵ (msec) and LF/HF Ratio⁶)
- Respiration (average respiration rate)
- Activity Classification (activities – standing, sitting, lying, walking and other)
- Activity Parameters - total step counts in a 6 minute walk test
- Sleep (sleep onset time (hours, minutes, and seconds), sleep wake time (hours, minutes, and seconds))
- Posture Classification (sleep posture, stationary posture standing, stationary posture sitting)

For each endpoint, the BioStamp nPoint measurements will be compared to a similar FDA approved measurement device, to other basic or manual measurement devices, or to independent observer measurements. The FDA approved measurement devices for this study are the Actiheart heart rate reference device and the Capnostream portable respiratory monitor. Table 10 displays the comparator method for each endpoint category.

Table 10: Endpoint Variable Group and Measurement Comparator

| Index | Endpoint Variable Group | Measurement Comparator |
|-------|-------------------------|-----------------------------|
| 1 | Heart Rate | Actiheart Device |
| 2 | Heart Rate Variability | Actiheart Device |
| 3 | Respiration | Capnostream Device |
| 4 | Activity Classification | Independent Observer |
| 5 | Activity Parameters | Manual Step Counting Device |
| 6 | Sleep Parameters | Independent Observer |
| 7 | Posture | Independent Observer |

Individual independent observers will receive training on the operation of all devices and execution of the study protocol before the enrollment of any subjects.

For heart rate and heart rate variability, the values collected will be the one minute average heart rate, the one minute RMSSD, and the five-minute LF/HF ratio from the BioStamp nPoint and the one minute average heart rate, the one minute RMSSD, and five minute LF/HF from the Actiheart device on each of six recording times for each subject. Two readings will be taken while the subject is at rest, two while exercising and two while lying down. These readings will be collected during the activities listed in Table 7 and Table 8.

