For respiration rate, the average resting respiration rate values will be collected at one minute time intervals during sleep on each subject using both the BioStamp nPoint and the Respiration Reference Device.

For the activity classification variable, each subject will be presented with five tasks (standing, sitting, lying, walking and stationary bike riding) in varied order and the activity classification will be recorded by the BioStamp nPoint and by the independent observer. This procedure will be repeated five times for each subject.

⁵ RMSSD: root-mean-square of successive difference of the time intervals between successive heartbeats.

⁶ LF/HF ratio: the ratio of power in the low-frequency (LF, 0.04-0.15 Hz) and high-frequency (HF, 0.15-0.4 Hz) bands of heart rate variability in the frequency domain.

For the exercise parameter “number of steps taken”, the number of steps taken by the subject during a 6 minute walk test will be recorded using both the BioStamp nPoint and a simple step counting device. This procedure will be repeated five times for each subject.

For the sleep parameters sleep onset time and wake time, the BioStamp nPoint values and independent observer values will be collected on each night and morning at the study site.

Posture classification variables will be analyzed separately for each type of posture activity (sleep positions, stationary posture standing and stationary posture sitting). For a given posture activity, the posture classification will be recorded by the BioStamp nPoint and the independent observer for two repeats each of each ground-truth posture for each subject. Each repeat will generate 5 independent observations of posture. The posture classifications for each posture classification variable are given in Table 11.

Table 11: Posture Variable vs Classification

| Index | Posture Variable | Posture Classification |
|-------|-----------------------------|---|
| 1 | Simulated sleep positions | Supine, prone, left side and right side |
| 2 | Stationary Posture Standing | Upright, lean left, lean right, lean back, lean forward |
| 3 | Stationary Posture Sitting | Upright, lean left, lean right, lean back, lean forward |

Sensor adhesion to the subject will be measured on a 4 point scale by the independent observer for each of four sensor patches on each subject following 24 hours of continuous wear. The adhesion rating scale is presented in Table 3.

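### Sections 4.1 and 11.3 analyse two repeats of five independent observations per posture where Table 7 performs five one-minute holds, and 11.3 draws lying five-minute LF/HF from tables with no lying item longer than one minute

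*Protocol*

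**What the plan says.** **Posture.** Sections 4.1 and 11.3 both say that device and observer classifications are recorded for "two repeats each of each ground-truth posture for each subject", and then: "Each repeat will generate 5 independent observations of posture". The procedure differs. Section 8.8.3 states: "This set of activities will be performed 5 times in a random order each time". Table 7 lists the 14 posture items (items 4 to 17) at one minute and five repetitions each. Staff mark the start and stop of each activity, and "The particular activity performed for a given annotation will be noted on the CRF". Table 5 schedules this set of activities once, on Day 0. Section 11.6.2 summarises categorical pairs by a two-way table and an agreement percentage.

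**LF/HF.** Section 11.3 asks for a one-minute heart rate, a one-minute RMSSD and a five-minute LF/HF ratio from both devices at six recording times per subject: "Two readings will be taken while the subject is at rest, two while exercising and two while lying down". It then names the source: "These readings will be collected during the activities listed in Table 7 and Table 8". The supine classification item in Table 7 reads "Once the subject is lying in a supine position, start the activity. | 1 min | 5", and the four lying posture items (14 to 17) have the same duration and repetitions. Table 8 begins with "Sit comfortably in a chair | 22 min | At least 2, up to 4" and otherwise contains only walking and biking.

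**The concern.** For posture, the analysis text and the procedure disagree on how many repeats exist, and the unit of observation is unclear. Posture classification is an effectiveness endpoint in a study described as pivotal for a 510(k) submission, and agreement percentage is its only planned numerical summary. If the number of repeats, the choice of repeats and the number of observations per repeat are all open, two analysts could follow the protocol faithfully and report different denominators. The word *independent* adds a second problem. Readings taken within one held posture share the subject, the posture and apparently the reference label, so they cannot be independent of one another.

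For LF/HF, the required window is longer than any lying activity in the tables from which the reading is to be taken. Followed literally, the lying third of the LF/HF data cannot be collected, and the complete-case rule in section 11.7 would leave the comparison with resting and exercising pairs only.

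**Working it through.** **Posture: inputs**
- Ground-truth postures: 4 sleep positions + 5 standing + 5 sitting = 14 (Table 11; Table 7 items 4 to 17).
- Repeats: 2 (sections 4.1 and 11.3) against 5 (section 8.8.3 and Table 7).
- Observations per repeat: 5 (sections 4.1 and 11.3) against one annotation and one CRF entry (section 8.8.3).
- Subjects: 25, the planned minimum (section 11.2).

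**Posture: counts**
1. The protocol's own figure per posture per subject is 2 × 5 = 10. Table 7 as described gives 5 × 1 = 5. The stated figure is not reproduced.
2. Holds covered by the analysis text: 2 × 14 × 25 = 700. Holds performed: 5 × 14 × 25 = 1,750. Unused: 1,750 − 700 = 1,050, and 1,050 / 1,750 = 60%.
3. Entries in the standing or the sitting table (5 postures): 10 × 25 × 5 = 1,250 by the analysis text, against 5 × 25 × 5 = 625 labelled holds. Sleep positions (4 postures): 10 × 25 × 4 = 1,000 against 5 × 25 × 4 = 500.
4. Could two sessions of five repetitions explain 2 × 5? No. Table 5 marks the activity classification set once, and the Day 1 text (section 8.8.10, Subject Training, and section 8.9) repeats only Table 8.
5. Could *two* be loose wording for all repeats? This is unlikely. Section 11.3 states five repeats for activity classification and for step counts, which come from the same Table 7 session.

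The discrepancy runs in opposite directions depending on the unit: the text uses too few holds (700 against 1,750) and claims more observations than there are labelled holds (2 × 5 × 14 × 25 = 3,500 against 1,750). Neither count can be recovered from the other.

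**LF/HF: inputs and counts**
- Window needed: 5 minutes. Longest lying item in Table 7 (items 3 and 14 to 17): 1 minute. Lying items in Table 8: none.
- Planned pairs: 6 × 25 = 150. Lying pairs: 2 × 25 = 50, and 50 / 150 = 33%. Pairs with a usable source item: 150 − 50 = 100.
- Rest is covered by the 22-minute sitting item. Exercise is covered by the 6-minute walk and 8-minute bike items in Table 7 and the 22-minute items in Table 8. Only lying falls short.
- Lying one-minute heart rate and RMSSD are obtainable: 5 items × 5 repetitions = 25 one-minute lying recordings per subject.

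**The case against.** The strongest reply is that these are wording conflicts with limited consequence. Several parts of it stand.

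- For categorical pairs, section 11.6.2 plans no interval, test or acceptance threshold; its sentence on standard deviations belongs to the continuous comparisons. A reader might infer that the posture result will be biased or its precision overstated. The documents do not support that. With equal numbers of readings per hold, correlation within a hold does not bias an agreement percentage, and understated uncertainty would arise only if an interval or SD were added.
- That each hold has a single observer label is an inference from one annotation and one CRF entry per activity. The five observations may be device outputs within the minute, and dividing a minute into epochs is ordinary SAP content. That would explain the number five but not the word *independent*, and it leaves two repeats against five.
- A count of 25 per posture per subject (5 × 5) can be formed only by joining Table 7's repeats to section 11.3's observations per repeat. No section states it, so it is not relied on here.
- A reader might infer that no lying LF/HF data will exist. That is too strong. The section on applying the heart rate reference device says heart rate is monitored throughout the study, both devices are worn overnight, and section 4.1 gives the same six readings without the table restriction. The fault is confined to the source that section 11.3 names.
- A reader might also fear that missing lying pairs would go unseen. Nothing in section 11.7 suppresses pair counts, and the planned plots show each pair.

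What does not stand is the suggestion that the SAP can settle everything. Whichever repeat count or lying source it adopts, it must depart from an explicit protocol sentence.

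**Conclusion.** Wrong as written on two points.

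(a) The posture analysis text does not match the procedure: two repeats against five, and 10 stated observations against 5 labelled holds per posture per subject. At n = 25, 60% of the holds performed would go unused, with no rule for choosing the two that count, so the denominator of the agreement percentage is not fixed. The claim of independence within a repeat is incorrect for readings from one held posture. This rests on reading the single annotation and CRF entry as the only observer label for a hold.

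(b) Two of six LF/HF readings per subject, 50 of 150 pairs at n = 25, cannot come from the tables that section 11.3 names. Lying heart rate and RMSSD are unaffected.

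Both should be corrected. Neither shows bias in a planned estimate, and neither calls for more subjects.

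**What to change.** 1. In sections 4.1 and 11.3, reconcile the repeat count with Table 7. The simplest repair is to use all five scheduled repeats, since they are performed anyway and no selection rule is then needed.
2. In the same sections, delete *independent* and state the unit of observation: either one classification per hold (5 per posture per subject) or several device readings per hold, with the number given. If any SD or interval is reported for posture, treat the subject as the cluster.
3. In section 11.3, either drop lying from the LF/HF endpoint while keeping lying heart rate and RMSSD, or name a continuous lying recording of at least five minutes as its source. The overnight recording already made with both devices is one candidate; the text should then say whether the subject must be awake.

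The cost is wording in two sections. All five posture repeats are already scheduled. Lying LF/HF needs no new recording if it is dropped or taken overnight; a dedicated recording would add about 2 × 5 = 10 minutes per subject.

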11.4 Analysis Populations

The following analysis populations will be defined for the study:

- Intent-to-Measure (ITM) Population – The ITM population will consist of all subjects who are enrolled in the study and for which the ability of each measurement device to measure the subject has been established.
- Safety Population – The safety population will consist of all subjects who are enrolled in the study.

The ITM population will be the primary analysis set for all effectiveness analyses. The safety population will be used for the analysis of all safety variables and baseline characteristics.

11.5 Analysis Subgroups

There is no subgroup analysis planned for the study.

11.6 Statistical and Analytical Plans

11.6.1 Disposition and Demographics

A table will be constructed with counts and percentages of the number of subjects who were screen failures, the number of subjects enrolled in the study, the number of subjects withdrawn from the study before study completion, and the number who completed the study. For those subjects who withdrew before completion of the study, counts and percentages of the reasons for withdrawal will be tabulated.

The continuous demographic characteristics at screening will be summarized for all subjects in the safety population using descriptive statistics (mean, standard deviation, median, minimum, maximum, and number of non-missing observations). The categorical baseline characteristics will be summarized for the safety population using frequency counts and percentages.

11.6.2 Effectiveness Endpoint Analyses

For pairs of measurements collected on the continuous scale (quantitative to quantitative comparisons), scatter plots with the 45 degree line of agreement superimposed will be constructed from paired observations from the two sources (BioStamp nPoint vs comparator) along with Bland-Altman plots of the data. The mean absolute error (MAE) and the root-mean-square error (RMSE) estimates of agreement will be calculated for each comparison. The standard deviations of each of the agreement measures will also be computed.

For pairs of measurements collected on a categorical scale (qualitative to qualitative comparisons), two-way tables of agreement will be constructed for each comparison. The agreement percentage will be computed for each table.

The number and percentage of sensor patches in each category of the adhesion scoring scale will be tabulated.

The statistical analyses of the effectiveness data will also be described in the Statistical Analysis Plan (SAP) for the study. The SAP will be written and finalized prior to database lock.

11.6.3 Safety Analysis

Prior to analysis, all AEs will be coded using the MedDRA coding dictionary. Based on these coded terms, TEAEs will be summarized using system organ class and preferred terms, as well as by relationship to the study devices. All AEs will be listed, regardless of whether or not they were study treatment related.

11.7 Handling Missing Data

In the statistical analysis of the primary effectiveness endpoints of the study, only the time points for each subject with evaluable endpoints for the both the BioStamp nPoint and the comparator method will be used in the statistical analysis, i.e., a complete case analysis. The handling of missing values for all other study endpoints will be described in the SAP for the study.

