3.0 STUDY PURPOSE AND OBJECTIVES

The purpose of this pivotal study is to evaluate the performance, usability, and reliability of the BioStamp nPoint system for continuous collection of physiological data in remote (in-home) and healthcare (in-clinic) settings.

The primary objective of the clinical investigation is to evaluate the accuracy of the BioStamp nPoint system algorithm measurements and to evaluate the adhesion (reliability) of the Sensors.

Safety and tolerability will be further assessed via a follow-up telephone call.

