In addition, sensor adhesion to the subject will be measured on a 4 point scale by the independent observer for each of four sensor patches on each subject following 24 hours of continuous wear. The adhesion rating scale (Table 3) is as follows:

Table 3: Sensor Adhesion Rating Scale

| Score | Rating | Description |
|-------|--|---|
| 0 | = ≥90% adhered | essentially no Sensor lift off the skin |
| 1 | = ≥75% to <90% adhered | some edges only of the Sensor lifting off the skin |
| 2 | = ≥50% to <75% adhered | less than half of the Sensor lifting off the skin |
| 3 | = >0% to <50% adhered but not detached | more than half of the Sensor lifting off the skin without falling off |
| 4 | = 0% adhered – Sensor detached | Sensor completely off the skin |

Usability will also be assessed by the clinician observing the subject using the system and via a subject questionnaire.

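### Under 11.7, missing BioStamp output cannot worsen any accuracy or agreement result, and beyond adhesion the protocol sets no measure of how often the device delivered a value

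*Protocol*

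**What the plan says.** Section 3.0 of the protocol gives the purpose as to "evaluate the performance, usability, and reliability of the BioStamp nPoint system for continuous collection of physiological data" in home and clinic settings. The primary objective that follows is narrower: to "evaluate the accuracy of the BioStamp nPoint system algorithm measurements and to evaluate the adhesion (reliability) of the Sensors".

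Section 11.7 sets the missing-data rule for the primary effectiveness endpoints, without singling any endpoint out as primary: "only the time points for each subject with evaluable endpoints for the both the BioStamp nPoint and the comparator method will be used". It calls this a complete case analysis. Other endpoints are deferred: "The handling of missing values for all other study endpoints will be described in the SAP for the study".

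Section 11.6.2 names the summaries. For continuous pairs: "The mean absolute error (MAE) and the root-mean-square error (RMSE) estimates of agreement will be calculated for each comparison". For categorical pairs, two-way tables are built and "The agreement percentage will be computed for each table". For adhesion: "The number and percentage of sensor patches in each category of the adhesion scoring scale will be tabulated". The worst adhesion category, score 4 in Table 3, is "Sensor completely off the skin".

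Sections 4.1, 11.3 and 11.6.2 set no summary of the share of reference time points at which the BioStamp returned a value.

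**The concern.** The rule treats two different events as one. If the comparator is missing there is nothing to compare against, and the point has to go. If the comparator is present and the BioStamp returns nothing evaluable, the device has failed to do what is being tested. Once both are removed, the accuracy and agreement figures describe only the moments at which the device produced output.

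This matters because the study is described as pivotal for a 510(k) submission, and continuous collection appears in both the purpose and the indications for use. Two devices with equal accuracy when they report, one reporting all night and the other half the night, would have the same expected MAE and RMSE. If output is lost mainly when measurement is hard, the device that reports less would look better.

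**Working it through.** The plan states no figure to reproduce. The check is of what the rule does, followed by illustrations. All rates of missing output, agreement levels and error sizes below are assumptions.

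**1. Agreement percentage.** Inputs from the protocol: 25 subjects (7.1), 5 tasks and 5 repeats (11.3), so 25 × 5 × 5 = 625 scheduled activity classifications. Assume every one has an observer value. Let *a* be agreement among activities the device classifies and *m* the share with no output.

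- Rule in 11.7: agreeing pairs / evaluable pairs = *a*(1 − *m*) / (1 − *m*) = *a*. The share *m* cancels.
- No output counted as non-agreement: agreeing pairs / all comparator-evaluable points = *a*(1 − *m*).

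With *a* = 0.95:

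| No output | Rule in 11.7 | No output as non-agreement |
|---|---|---|
| 5% | 95% | 0.95 × 0.95 = 0.9025 (90.3%) |
| 10% | 95% | 0.95 × 0.90 = 0.855 (85.5%) |
| 20% | 95% | 0.95 × 0.80 = 0.760 (76.0%) |

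In counts, at 20%: 500 are classified and 475 agree. That is 475/500 = 95% under the plan and 475/625 = 76% with the lost points kept in the denominator.

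**2. MAE and RMSE.** Assume heart-rate errors are normal with mean zero, SD 2 bpm in 80% of minutes and SD 10 bpm in 20%. For such an error, the mean absolute value is SD × √(2/π) = 0.798 × SD.

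- No loss: MAE = 0.798 × (0.8 × 2 + 0.2 × 10) = 2.87; RMSE = √(0.8 × 4 + 0.2 × 100) = 4.82.
- 10% of minutes lost, all from the noisy part: MAE = 0.798 × (0.8 × 2 + 0.1 × 10) / 0.9 = 2.30; RMSE = √((3.2 + 10) / 0.9) = 3.83.
- 20% lost, all from the noisy part: MAE = 0.798 × 2 = 1.60; RMSE = 2.00.

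A simulation of 200,000 minutes gave nearly the same values: MAE 2.86, 2.29 and 1.59; RMSE 4.80, 3.80 and 2.00. Loss at random left MAE at 2.86. So in this model random loss leaves the result unchanged, and loss in difficult minutes improves it.

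**3. Adhesion.** With 4 sensors on each of 25 subjects there are 100 patches, so each detached sensor adds 1 percentage point to category 4. Detachment therefore does show. But adhesion is scored by eye from the attached surface (8.8.6), and the shank and forearm sensors collect no data (6.2). An attached sensor that loses its signal scores 0, the best category.

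**The case against.** The strongest defence is that the protocol gives reliability its own meaning. The primary objective equates it with adhesion, and adhesion is analysed in full under Effectiveness Endpoint Analyses. A reader might infer from 11.7 that device drop-out cannot lower any effectiveness result, or that the trial cannot address reliability at all. The documents do not support either reading: a detached sensor is counted in score 4. What remains is loss of output from a sensor that is still attached.

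Second, MAE, RMSE and Bland-Altman plots need both values, so restricting them to pairs is unavoidable. That stands, and no change to it is proposed. The denominator is open to choice only for the activity and posture tables.

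Third, 11.7 does not forbid reporting counts of missing pairs, and the SAP, which was not available, may do so. The activity schedule is also fixed, so a shortfall in those table totals would be visible. This is fair: it cannot be said that losses will go unreported. But the protocol itself fixes the complete-case rule for these endpoints and leaves only the others to the SAP. A yield table in the SAP would not change the agreement percentage set here.

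Fourth, the protocol does not say that the classifier can return no class. An output of 'other' for a standing subject would already count as disagreement. Nor does anything in the protocol show that loss clusters in difficult periods. Both points stand: the sizes above are illustrations, and the flattering effect is conditional.

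**Conclusion.** The point holds for the accuracy and agreement results. Under 11.7, a comparator-evaluable point with no BioStamp value leaves MAE, RMSE and agreement percentage without penalty. For the agreement percentage this follows from the algebra: the share of missing output cancels whatever its value. MAE and RMSE do not penalise the loss either, and whether they improve depends on where it falls, which the protocol does not tell us.

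The size cannot be known from the document, which gives no rate of missing output. At an assumed 95% agreement and 5% to 20% no output, the gap is 4.75 to 19 percentage points (95 − 90.25 and 95 − 76). If output is nearly complete, the gap is negligible, and a reported yield would show that.

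The purpose of reliability for continuous collection is partly addressed through adhesion, and not otherwise. This is an inexpensive improvement to a stated rule rather than a flaw that invalidates the study.

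**What to change.** - **11.7:** separate the two cases. Drop points with a missing comparator. Count points where the comparator is evaluable and the BioStamp value is not.
- **11.6.2, every endpoint compared with a reference:** report BioStamp yield, meaning comparator-evaluable points with a BioStamp value divided by all comparator-evaluable points, per subject and overall.
- **11.6.2, activity and posture tables:** add a no-output column, and give the agreement percentage with no output counted as non-agreement beside the complete-case figure.
- **MAE and RMSE:** keep on paired points, always shown with the yield.

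The yield depends on what counts as evaluable, so that definition should be settled before the two data streams are matched.

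The cost is a few sentences and one extra column per categorical table. No new procedures or data are needed, because section 12.1 already archives all analytic outputs and all ground-truth data. The one downside for the sponsor is that reported agreement may be slightly less favourable.
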